8.1.1 Post Study Treatment Study Follow-up

Subjects who discontinue study treatment will continue to be followed for 28 days post last dose of study medication.

8.2 Discontinuation from the Study

Subjects who request to discontinue study treatment (possible circumstances are listed in [Section 8.1](#)) will remain in the study and must continue to be followed for protocol-specified follow-up procedures. The only exception to this is when a subject specifically withdraws consent for any further contact with him/her or persons previously authorized by subject to provide this information.

- Subjects should notify the investigator of the decision to withdraw consent from future follow-up **in writing**, whenever possible.
- The withdrawal of consent should be explained in detail in the medical records by the investigator and entered on the appropriate eCRF page.
- In the event that vital status (whether the subject is alive or dead) is being measured, publicly available information should be used to determine vital status only as appropriately directed in accordance with local law.
- If the subject withdraws consent for disclosure of future information, the Sponsor may retain and continue to use any data collected before such a withdrawal of consent.

8.2.1 Temporary IP Discontinuation

The following criteria for temporary interruption of study treatment apply:

- For those subjects who present with signs and/or symptoms of COVID-19 during the study, the study treatment should be temporarily interrupted while the subject undergoes diagnostic testing for SARS-CoV-2 (see [Section 9.10](#)).
- Study treatment must be temporarily interrupted for subjects who test positive for SARS-CoV-2 until complete recovery (if symptomatic), and a negative molecular test result is obtained. Study treatment may be restarted at investigator discretion following consultation with the BMS medical monitor/designee provided that the subject meets the criteria outlined in [Section 9.10](#).

8.3 Discontinuation of the Study/Study Stopping Rules

There will be a DMC to provide oversight of the safety in this trial as outlined in [Section 5.1.5](#) of the protocol. The DMC is responsible for assessing the ongoing acceptability of the benefit/risk profile for the study drug in an unblinded manner. Subjects, investigators, site staff, and the Sponsor study team all remain blinded to study treatment throughout the conduct of the trial.

- The DMC will review unblinded study treatment information and safety data to adjudicate study treatment relatedness and to make a recommendation regarding the appropriateness of continuing the study, with or without study modifications, or stopping the study in the event that either of the following occur:
- 2 or more subjects experience an SAE of the same preferred term and that is considered related to the study treatment by the investigator (for example, not explained by underlying or intercurrent medical condition or concomitant medication)
- 2 or more subjects are discontinued due to the same laboratory parameter abnormality as defined by the criteria in [Section 8.1](#)

8.4 Lost to Follow-up

- All reasonable efforts must be made to locate subjects to determine and report their ongoing status. This includes follow-up with persons authorized by the subject.
- Lost to follow-up is defined by the inability to reach the subject after a minimum of 3 documented phone calls, faxes, or emails as well as lack of response by subject to 1 registered mail letter. All attempts should be documented in the subject's medical records.
- If it is determined that the subject has died, the site will use permissible local methods to obtain date and cause of death.
- If investigator's use of third-party representative to assist in the follow-up portion of the study has been included in the subject's informed consent, then the investigator may use a Sponsor retained third-party representative to assist site staff with obtaining subject's contact information or other public vital status data necessary to complete the follow-up portion of the study.
- The site staff and representative will consult publicly available sources, such as public health registries and databases, in order to obtain updated contact information. If after all attempts, the subject remains lost to follow-up, then the last known alive date as determined by the investigator should be reported and documented in the subject's medical records.

8.5 Replacement of Subjects

Subject replacement is not permitted.

9 STUDY ASSESSMENTS AND PROCEDURES

Study procedures and timing are summarized in the Schedule of Activities ([Section 2](#)). Waivers or exemptions from protocol-required evaluations are not allowed.

All immediate safety concerns must be discussed with the medical monitor immediately upon occurrence or awareness to determine if the subject should continue or discontinue treatment.

Adherence to the study design requirements, including those specified in the Schedule of Activities ([Section 2](#)), is essential and required for study conduct.

All screening evaluations must be completed and reviewed to confirm that potential subjects meet all eligibility criteria before randomization. The investigator will maintain a screening log to record

details of all subjects screened and to confirm eligibility or record reasons for screening failure, as applicable.

Procedures conducted as part of the subject's routine clinical management (eg, blood count) and obtained before signing of the ICF may be used for screening or baseline purposes provided the procedure meets the protocol-defined criteria and has been performed within the time frame defined in the Schedule of Activities ([Section 2](#)).

The study data includes all the information that is collected as a result of the study, including subject demographics, disease characteristics, clinical information, blood tests, [REDACTED], endoscopic videos, intestinal biopsies obtained during endoscopy, and other tests listed in [Section 2](#). Study data collected during this study will be used to help understand how BMS-986165 works in people with CD and related health conditions. The study data may also be used to help understand the biology of CD and related health conditions, study test performance in people with CD, and for other relevant health research relating to BMS-986165 or these health conditions.

9.1 Efficacy Assessments

Every effort must be made to ensure that the same evaluator(s) complete the assessment for each subject. If the evaluator(s) is unable to complete the evaluation, then a qualified individual with overlapping experience may perform the evaluation. Documentation of who performed the evaluation is to be recorded in source documents. Assessments are to be performed at approximately the same time of day throughout the duration of the study.

Baseline assessments must be performed per protocol (standard of care assessments may not be used for baseline). Procedures not specified in the protocol that are part of standard care may be performed if they do not interfere with study procedures; any data arising from such procedures are not to be reported in the eCRF.

The following procedures or tools will be used to assess subjects' CD activity during the study (see schedule in [Section 2](#)):

- CDAI^{10,15,16} ([APPENDIX 10](#)) and PRO2¹² ([REDACTED]): The CDAI and PRO2 scores will be calculated using 7 days of subject diary entries. CDAI also includes additional components, as outlined in [APPENDIX 10](#). The following rules apply to the calculation of CDAI and PRO2 scores:

For Week 0, if there are < 14 days between the endoscopy date and the visit date, the bowel preparation day will serve as the diary reference point; if there are ≥ 14 days between the endoscopy date and the visit date, the Week 0 visit date will serve as the diary reference point.

- The collection window for subject diary data used for the calculation of CDAI and PRO2 scores for a study visit (other than Week 0) should be a maximum of 14 days prior to the day of the study visit. For study visits that include endoscopy, the final day of diary collection is the day before the subject starts bowel preparation for ileocolonoscopy.
- CDAI/PRO2 calculation will be performed using the 7 latest days of diary entry in the collection window. These days do not have to be consecutive. At least 4 of those 7 days of diary data must be collected in the final 7 days of the collection window. If either of these criteria are not met, the CDAI/PRO2 score will be counted as “missing.”

- If the requirements outlined above are not met, CDAI/PRO2 cannot be calculated for that study visit. If this occurs prior to the Week 0 visit, the subject cannot meet Inclusion Criterion 2)f), cannot be randomized, and must be screen-failed.
- Prior to each scheduled visit at which CDAI/PRO2 is to be calculated, determine whether an adequate number of diary entries have been made. If adequate entries have not been made, the site should contact the subject to reschedule the visit (or endoscopy, if applicable), and the subject should be counseled about proper study procedures.
- SES-CD¹⁷ (APPENDIX 12): The SES-CD assesses the size of mucosal ulcers, the ulcerated surface, the endoscopic extension, and the presence of stenosis. This blinded assessment will be carried out by Alimentiv Clinical Trials, and the results will be considered final for this study.

- [REDACTED]

- [REDACTED]

- [REDACTED]

- [REDACTED]

- [REDACTED]

- [REDACTED]

- [REDACTED]

- [REDACTED]

- [REDACTED]

- [REDACTED]
- [REDACTED]
- [REDACTED]

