5.1.2 Induction Period

On Day 1 of the Induction Period, subjects who have completed the screening procedures and met the inclusion/exclusion criteria will be randomized in a 3:3:2 ratio to receive oral BMS-986165 6 mg BID or 3 mg BID or placebo BID, respectively, [redacted]

[redacted]

Video ileocolonoscopy examination and collection of ileal and/or colonic tissue biopsies should be performed within a window of 7 days prior to the Week 12 visit. Note: This requirement will

also apply to subjects who terminate early and have received study treatment for at least 4 weeks. The study diary requirements for the calculation of CDAI/PRO2 are outlined in [Section 9.1](#).

Clinical response will be assessed at Week 12 (Section 5.1.3) to determine whether subjects will continue on the initially assigned double-blind dose or be offered the opportunity to switch to open-label BMS-986165 6 mg BID for the Maintenance Period. Subjects who were randomized prior to the implementation of Protocol v3.0 who have not yet reached Week 12 will likewise be offered the opportunity to switch to open-label BMS-986165 6 mg BID for the Maintenance Period, if they do not achieve a clinical response at Week 12.

If, in the opinion of the investigator, a subject requires rescue therapy for CD during the Induction Period, the subject must permanently discontinue study treatment, complete an ET Visit and enter the Post-treatment Follow-up Period. Examples of rescue therapies that are prohibited in this study include prednisone > 20 mg QD PO (or equivalent), intramuscular (IM) or IV corticosteroids, and biologic therapies that are approved for the treatment of CD in at least 1 country ([REDACTED] and [Section 7.7.1](#)). Endoscopy is required at the ET Visit for subjects who permanently discontinue study medication between Weeks 4 and 12. Discontinuation criteria are further detailed in [Section 8](#).

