5.1.3.5 Week 52 (Day 365)

Video ileocolonoscopy examination and collection of ileal and/or colonic tissue biopsies should be performed within a window of 7 days prior to the Week 52 visit. The study diary requirements for the calculation of CDAI/PRO2 are outlined in [Section 9.1](#).

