5.1.4 Open-label Extension Period

[figure not shown]
[figure not shown]
Subjects who continue to derive a clinical benefit from IP at Week 52, as judged by the investigator, are eligible to enter the OLE Period. The OLE Period will last 52 weeks, to Week 104. Study visits in this period occur every 4 weeks for the first 3 months, then approximately every 3 months afterwards, to Week 104. The final ileocolonoscopy will occur within a window of 7 days prior to the Week 104 visit. The study diary requirements for the calculation of CDAI/PRO2 are outlined in Section 9.1.

[figure not shown]
[figure not shown]
Subjects who require prohibited rescue treatment for CD (see [REDACTED] and [Section 7.7.1](#)) during the OLE Period must permanently discontinue study treatment, complete an ET Visit, and enter the Post-treatment Follow-up Period. An exit endoscopy is recommended for all subjects who undergo an ET Visit between Week 56 and Week 104. This is not required for ET Visits within 4 weeks of the Week 52 endoscopy.

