10.4.2 Imputation Methods for Co-primary Endpoints

Non-responder imputation (NRI) will be used for co-primary efficacy endpoints for subjects who discontinue treatment prior to Week 12 and have no Week 12 assessments after treatment discontinuation, [REDACTED] initiate use or continue to use prohibited medications in the Induction Period, require surgical procedure(s) for treatment of CD or related complications in the Induction Period, or have otherwise missing endpoint data at the Week 12 (Day 85) timepoint, ie, the NRI will be the primary method of imputation for the co-primary efficacy endpoints.

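### At endoscopy visits the diary window can hold only 6 of the 7 days that CDAI and PRO2 need, so a complete diary can still end as an imputed non-response at Week 12

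*Combined protocol and SAP*

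**What the plan says.** Protocol Section 9.1 sets the diary rules for CDAI and PRO2:

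- Opening: the collection window "for a study visit (other than Week 0) should be a maximum of 14 days prior to the day of the study visit".
- Closing, at visits with endoscopy: "the final day of diary collection is the day before the subject starts bowel preparation for ileocolonoscopy".
- Selection: "CDAI/PRO2 calculation will be performed using the 7 latest days of diary entry in the collection window". The days need not be consecutive, but at least 4 of the 7 must fall in the last 7 days of the window. If either condition fails, the score is missing.
- Site check: before each such visit, sites are to "determine whether an adequate number of diary entries have been made" and, if there are too few, should reschedule the visit or the endoscopy.

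Endoscopy is to be "performed within a window of 7 days prior to the Week 12 visit" (Section 5.1.2). Section 5.1.3.5 has the same allowance for Week 52 ("performed within a window of 7 days prior to the Week 52 visit"), and Section 5.1.4 for Week 104 ("within a window of 7 days prior to the Week 104 visit"). Table 2 gives the Week 12 visit a window of 3 days either way.

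Section 10.4.2 applies non-responder imputation to the co-primary endpoints of subjects who "have otherwise missing endpoint data at the Week 12 (Day 85) timepoint". Section 10.4.5 does the same for the binary secondary endpoints.

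Only Week 0 has a diary reference point tied to bowel preparation, used when endoscopy is less than 14 days before the visit.

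**The concern.** The window opens at a point fixed by the visit and closes at a point fixed by bowel preparation. Each day that endoscopy moves earlier therefore removes a usable diary day. At the early edge of the permitted endoscopy window, the days left can fall below the number the score requires.

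A subject who completes every diary entry and is in remission could then be counted as a failure on clinical remission, clinical response and PRO2 remission, because of scheduling and not disease. Week 12 clinical response also decides whether a subject stays on blinded treatment (Section 5.1.3.1), so a score that cannot be calculated matters at the site as well.

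The loss does not depend on arm. It does not inflate type I error and does not touch the endoscopic co-primary endpoint. What it does is shrink the observed differences in the CDAI and PRO2 endpoints, and with them the power.

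**Working it through.** **Inputs.** From the documents: the window opens on day -14 (Section 9.1); it closes the day before preparation starts (Section 9.1); 7 diary days are needed, at least 4 of them in the last 7 days of the window (Section 9.1); endoscopy falls *d* = 1 to 7 days before the visit (Sections 5.1.2, 5.1.3.5, 5.1.4); the arms have 90 and 60 subjects, tested at two-sided 0.025 (Section 10.1).

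Assumed: the preparation lead *g*, which the documents do not give. I use *g* = 0 (same day) and *g* = 1 (day before).

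**Usable days.** The last usable day is -(*d* + *g* + 1), so usable days = 14 - *d* - *g*.

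| Endoscopy day | -7 | -6 | -5 | -4 | -3 | -2 | -1 |
|---|---|---|---|---|---|---|---|
| Same-day preparation | 7 | 8 | 9 | 10 | 11 | 12 | 13 |
| Day-before preparation | 6 | 7 | 8 | 9 | 10 | 11 | 12 |

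With day-before preparation, day -7 leaves 6 days, fewer than the 7 required. Day -6 leaves exactly 7, with no room for a missed entry. With same-day preparation, day -7 leaves exactly 7. If the 14 days were counted to include the visit day (days -13 to 0), every figure would drop by one.

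**Moving the visit.** Take endoscopy on Day 78, day-before preparation and the visit due on Day 85 (6 usable days). A visit on Day 84, 83 or 82 gives 7, 8 or 9 days. A visit on Day 86 gives 5 and on Day 88 gives 3, with endoscopy by then outside its own 7-day limit. A shortfall can also arise wholly within the rules: endoscopy planned for day -4 (9 usable days) becomes day -7 (6 usable days) if the visit slips by the permitted 3 days.

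**Chance of a missing score.** Assume independent daily entries with completion rate *a*. A score needs at least 7 entries, with at least 4 in the last 7 days. With 7 usable days and *a* = 0.95, the chance of missing is 1 - 0.95^7 = 30.2%. With 8 usable days it is 1 - (0.95^8 + 8 × 0.05 × 0.95^7) = 5.7%. With 6 it is 100%. Averages over endoscopy days, with no rescheduling:

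| Scenario | *a* = 100% | 95% | 90% |
|---|---|---|---|
| Same-day, days -7 to -1 equally likely | 0% | 5% | 11% |
| Day-before, days -7 to -1 equally likely | 14% | 20% | 25% |
| Same-day, days -5 to -1 only | 0% | 0.2% | 1.5% |
| Day-before, days -5 to -1 only | 0% | 1.3% | 5.2% |
| 14 days ending the day before preparation | 0% | 0.02% | 0.3% |

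The 14% is simply 1/7: the share of endoscopies that the even spread places on day -7.

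**Power, for illustration.** The design response rates in Section 10.1 are redacted, so there is no planned figure to reproduce and the rates here are mine. With a fraction *m* missing and imputed as failure, both rates are multiplied by (1 - *m*). The pooled two-proportion formula is

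power = Φ( [|p1 - p2| - z·√(p̄(1-p̄)(1/90 + 1/60))] / √(p1(1-p1)/90 + p2(1-p2)/60) ), with z = 2.241.

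For 38% vs 15% and *m* = 0: p̄ = (34.2 + 9)/150 = 0.288, so (0.23 - 2.241 × 0.0755)/0.0689 = 0.88 and power is 81%.

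| Rates | *m* = 0% | 5% | 14% |
|---|---|---|---|
| 35% vs 15% | 69% | 66% | 59% |
| 38% vs 15% | 81% | 78% | 71% |
| 40% vs 15% | 87% | 84% | 78% |

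**The case against.** The strongest reply is that this is an edge case that the protocol already guards against. No passage says when preparation starts. If it starts on the day of endoscopy, a complete diary always gives a score; if the day before, only day -7 makes a score impossible. A site that applies Section 9.1 to a day -7 endoscopy would count 6 eligible days, find them inadequate and reschedule. Moving the visit one day earlier, or the endoscopy one day later, restores 7. The 14% to 25% figures ignore that instruction. With endoscopy on day -5 or later, day-before preparation and 95% completion, the loss is 1.3%, and power for 38% vs 15% falls only from 81.1% to 80.3%. The visit-anchored limit also keeps diary days close to the hematocrit, weight and other non-diary CDAI components. Finally, the SAP may already settle the derivation.

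Much of this stands as a limit on size. The larger percentages are worst cases, and the frequency is unknown. It does not remove the conflict. Even same-day preparation leaves no spare day at day -7. Rescheduling is worded as a recommendation, and the check asks about the number of entries without warning that endoscopy timing limits the window. Once endoscopy is done, later entries cannot count, and postponing the visit, a natural response to missing entries, shortens the window further. The file reviewed contains no SAP text, so whether the SAP resolves this cannot be checked; if it does, Section 9.1 should still be brought into line.

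**Conclusion.** The concern holds. As written, the opening rule, the closing rule, the 7-day requirement and the 7-day endoscopy window cannot all be met when endoscopy is on day -7 and preparation starts the day before. With no lead time stated, nothing in the plan excludes that case. At Week 12 the result is an imputed non-response on one co-primary and two secondary endpoints. At Weeks 52 and 104 the same rules can produce a missing score, but the imputation rules cited here cover Week 12 only.

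The size depends on how many endoscopies fall on days -7 and -6, how complete the diaries are, and how often sites reschedule. None of these is given. On the assumptions shown, missing scores range from 0% to about 25%. At the illustrative rates, 5% missing costs about 3 points of power and 14% missing about 9 to 10. This should be fixed, but it does not threaten the validity of the trial.

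**What to change.** Before the Week 12 database lock, state in Section 9.1, the SAP and the derivation program that at visits with endoscopy (Weeks 12, 52 and 104) the collection window is the 14 days ending the day before bowel preparation starts. Keep the rule of the 7 latest entries with at least 4 in the last 7 days of the window. This matches the preparation-day reference point used at Week 0, although that rule itself states no 14-day length.

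The cost is one sentence in each document and a change to the program. Subjects are expected to complete the diary daily throughout the study (Section 5.1), so no new data collection is needed. The downside is that some entries could be older: with endoscopy on day -7 and day-before preparation, the window runs from day -22 to day -9. The older entries are used only when the 7 latest are not available closer to the visit.

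Narrowing the endoscopy window would also reconcile the rules, but it could not recover scores for endoscopies already done. Making the change after unblinding would look post hoc.

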9.2 Laboratory Assessments

The following laboratory tests will be performed according to the Schedule of Activities in [Section 2](#) to gather more information about CD activity: [REDACTED]; stool *C. difficile*; quantitative immunoglobulins (IgM, IgE, IgA, IgG); T, B, and natural killer (TBNK) cells; and hematocrit (ie, for CDAI). For the purpose of prompt CDAI score calculation from Week 2 through Week 52 and at Week 104, the hematocrit may be performed by a local laboratory.

9.3 Adverse Events

The investigator and any designees are responsible for detecting, documenting, and reporting events that meet the definition of an AE or SAE and remain responsible for following up AEs that are serious, considered related to the study treatment or the study, or that caused the subject to discontinue before completing the study.

The definitions of an AE or SAE can be found in [APPENDIX 3](#).

[REDACTED]

[REDACTED]

9.3.1 Adverse Events of Interest

AEIs are AEs for a particular product or class of products that a Sponsor may wish to monitor carefully. AEIs may be serious or nonserious. Such events may require further investigation to better characterize and understand them. In the BMS-986165 clinical development program, certain skin-related AEs (eg, acne) and infection AEs have been identified as potential AEIs; however, there has been no definitive assessment on the causal relationship between these events and treatment with BMS-986165.

In addition, given that immunomodulation is consistent with the mechanism of action of BMS-986165, malignancies are considered to be an important potential risk of therapy with BMS-986165 and should be monitored as AEIs. Malignancies were not identified as adverse findings in nonclinical studies and no serious adverse reactions of malignancy have been reported to date in clinical studies of BMS-986165.

For purposes of reporting these AEIs, specialized eCRF pages will be required to collect additional information related to characterization, social/family history, risk factors, signs/symptoms, diagnostics, and treatments.

